4.10.5. Study variables

The study variables will make up the research instrument used to collect the data (see Appendix II).

Sociodemographic and clinical variables: gender, color, age, weight, height, underlying neoplastic disease, performance status and number of organs affected by metastases. Presence of fever, low back pain, pain at the wrist-percussion of the lumbar region, pain in the hypogastrium, dysuria and polyuria and presence of cloudy urine.

Radiological data: degree of urinary tract obstruction.

Dates of diagnosis of the underlying neoplasm and diagnosis of malignant ureteral obstruction.

Laboratory data: blood count, creatinine, urea, type I urine, uroculture and antibiogram.

Antibiotics: for the prophylaxis or treatment of urinary tract infection and sensitivity of the first antibiotic used for prophylaxis and/or treatment.

Colonizing and infecting agents and their classification in terms of multidrug-resistant organisms

Period of use of the catheter(s); removal of the catheter(s); other complications, such as mobility of the catheter(s) and/or obstructions.

4.11. Data Storage Plan

Information collection will be based on a structured collection instrument (Appendix II). The information will be sought from the institution's database, corroborated by consultations with medical records and local sector records.

The data will be stored on the REDCap Platform⁴⁷ which is among the best data collection, management and storage platforms for research and multi-institutional studies. It complies with the American laws on the protection of patient data, the *Health Insurance Portability and Accountability Act* (HIPAA). In addition to secure data storage and management, research data is stored on the institution's own server.

Formatado: Inglês (Estados Unidos)

Formatado: Inglês (Estados Unidos)

Formatado: Inglês (Estados Unidos)

Código de campo alterado

Código de campo alterado

4.12. Statistical Analysis

The data will initially be tabulated in an electronic spreadsheet in REDCap and for the statistical analysis, only the research team's statistician will download the data into the statistical program (SPSS). The study population will be characterized using descriptive statistics, using the mean, standard deviation, minimum, maximum and quartiles for quantitative variables and frequency tables for qualitative variables.

The database will be made up of patient information and procedure information, but with a unique identifier for each patient, allowing information to be linked between them.

For the purposes of this study, nephrostomy procedures will be considered independent. The procedures will be separated into first pass and catheter changes. In the first passage, procedures with antibiotic prophylaxis and without antibiotic prophylaxis will be studied. In catheter changes, procedures with empirical antibiotic prophylaxis and with targeted antibiotic prophylaxis will be studied. The types of procedures and the other characteristics of the procedures will be associated with the occurrence of urinary tract infection using the Chi-square test or Fisher's exact test, depending on the expected values in the contingency table. The multiple analysis will be carried out using Logistic Regression with multiple variables. To this end, only the variables with a p-value of less than 0.20 in the univariate analysis will be selected for the model.

The significance level will be 5%, two-sided, for all statistical analyses, which will be carried out using the SPSS v21 program.

Part II - Systematic Review and Meta-Analysis

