4.9. Sample size calculation

The retrospective cohort will be made up of 372 consecutive, non-probabilistic patients for convenience, according to data collected from the institution's hospital

system (SisOnco). These patients will be studied according to the procedures performed, divided into first catheter passage and catheter change.

In the first pass of the percutaneous nephrostomy catheter group, 372 procedures were carried out at the Barretos and Jales Cancer Hospitals. In the catheter change group, 358 procedures were carried out in the stipulated period. Totaling 730 procedures carried out at the two hospitals between January 2013 and June 2020.

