4.10.3. Procedure for changing the catheter

Catheter changes take place electively approximately every 90 days after the previous procedure (first pass or previous catheter change), scheduled during outpatient follow-up. However, this change can happen earlier than planned due to situations such as catheter obstruction and migration, or even catheter-related urinary tract infection.

This group will be made up of patients undergoing percutaneous nephrostomy catheter exchange and will study the use of empirical or targeted antibiotic prophylaxis documented in medical records to be reviewed at the two hospitals.

The Jales Cancer Hospital will study targeted antibiotic prophylaxis, which consists of collecting the following laboratory tests around 7 days before the procedure

to change the nephrostomy catheter(s) to guide the antibiotic to be used for prophylaxis: serum creatinine and urea levels, urine samples for tests such as urine summary (or type I urine) and uroculture with antibiogram. If the tests are not carried out prior to the procedure or if the uroculture does not show a specific bacterial agent, the procedure will be studied according to empirical antibiotic prophylaxis.

The Hospital de Câncer de Barretos will study the empirical antibiotic prophylaxis carried out according to daily clinical practice, recorded in the medical records to be reviewed of patients undergoing percutaneous nephrostomy catheter exchange.

The proportion of urinary tract infections that developed within 7 days of the procedure will be studied. A procedure-related urinary tract infection is considered to be any report in the medical record of clinical signs and symptoms associated with uroculture results (see definition in item 4.10.4.) and the location of the respective treatment will be documented: outpatient, inpatient or intensive care unit (ICU).

It will be documented whether there is evidence reported in medical records of urinary tract infections or the presence of bladder fistulas prior to the procedure.

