median, standard deviation, minimum, maximum and quartiles for quantitative variables and frequency tables for qualitative variables.

The database was made up of patient information and procedure information, but with a unique identifier for each patient, allowing information to be linked between them.

For the purposes of this study, nephrostomy procedures were considered independent.

The Shapiro-Wilk normality test confirmed the non-normal distribution of the continuous variables. These non-parametric variables were described as the median and the respective interquartile range (from the 25th to the 75th percentile). The Mann-Whitney test was used to compare two independent samples. Categorical variables were presented in absolute and relative frequencies using chi-square association tests or Fisher's exact tests when the expected result was less than five in more than 20% of the cells in the association tables. Post-hoc analysis was carried out using Bonferroni's adjusted p-value for comparisons between more than two independent groups of categorical variables. Multiple analysis was carried out using multiple variable logistic regression. To this end, only the variables that obtained a p-value of less than 0.20 in the simple logistic regression analysis were selected for the model. The analyses were carried out using IBM-SPSS v.26.0 software with a significant level of 5%, two-sided. G*Power v.3.1.9.4 software was used to calculate the statistical power of the sample in the analysis for urinary tract infection.

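### Repeat catheter changes are analysed as independent procedures; if infections cluster within patients, the guided-versus-empirical test and patient-level risk factors get standard errors that are too small

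*Protocol*

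**What the plan says.** Protocol 4.12 states "For the purposes of this study, nephrostomy procedures will be considered independent". The SAP, under Statistical analysis, repeats this in the past tense: "For the purposes of this study, nephrostomy procedures were considered independent".

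Infection is related to prophylaxis group and to other characteristics "using the Chi-square test or Fisher's exact test, depending on the expected values in the contingency table". Ordinary logistic regression follows, on variables that pass a p < 0.20 screen. One level covers everything: "The significance level will be 5%, two-sided, for all statistical analyses".

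Protocol 4.9 counts 372 patients and two sets of procedures: "In the first pass of the percutaneous nephrostomy catheter group, 372 procedures were carried out at the Barretos and Jales Cancer Hospitals", and "In the catheter change group, 358 procedures were carried out in the stipulated period". Protocol 4.10.3 says "Catheter changes take place electively approximately every 90 days after the previous procedure", and adds that the previous procedure may itself have been a change.

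The database holds patient and procedure records "with a unique identifier for each patient, allowing information to be linked between them". Neither document uses that link in the analysis. There is no GEE, random effect, cluster-robust variance or one-procedure-per-patient analysis, and no reason is given for assuming independence.

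**The concern.** Chi-square, Fisher and ordinary logistic regression treat each procedure as a separate piece of evidence. Several changes in one patient are not separate if that patient's infections resemble each other, and the protocol gives reasons to expect this. Section 1.5.1 describes biofilm as a reservoir that can prolong an infection or help start another. Section 1.5.2.3 cites an oncology cohort in which previous urinary infection was a main risk factor.

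Ignoring such correlation matters most when the compared factor is the same across a patient's procedures. Under 4.10.3, culture-guided prophylaxis is studied at Jales and empirical prophylaxis at Barretos, so prophylaxis type differs largely between patients. Tumour type and number of metastatic organs (4.10.5) are also mainly patient-level.

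Guided versus empirical prophylaxis at catheter change is one of the two questions that close section 1.5.2.3 and is part of the primary objective (3.1). Risk factors are a secondary objective (3.2). At the 11.4% infection rate after changes in the institution's earlier cohort (1.5.2.3), 358 changes give about 0.114 × 358 = 41 infections. With so few events, a handful of recurrently infected patients could produce a significant result.

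**Working it through.** **Inputs from the documents.** 358 changes, 372 patients and 372 first passes (4.9); two-sided 5% (4.12); 11.4% infection after changes (1.5.2.3).

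**Assumptions.** The documents give neither changes per patient nor ICC. Two cluster sizes are borrowed from studies that the protocol cites:
- Lower: 51% of patients in a cancer cohort had a catheter replaced (1.5.2.3). 0.51 × 372 = 190 patients; 358/190 = 1.88 changes each.
- Upper: 493 exchanges in 126 patients (1.5.2.2). 493/126 = 3.91 each; 358/3.91 gives about 92 patients.

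ICC is taken from 0.05 to 0.30.

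**Step 1: the plan's own figure.** Under independence the design effect is 1 and α = 2(1 − Φ(1.96)) = 5.0%. Simulating the planned test on 358 procedures from 358 different patients rejected in 4.9% of 10,000 runs. The counts agree: 372 + 358 = 730.

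**Step 2: prophylaxis type fixed within patient.** Design effect DE = 1 + (m_w − 1) × ICC, where m_w is the size-weighted number of changes per patient (equal to the mean if all patients have the same number). The standard error grows by √DE, and actual α = 2(1 − Φ(1.96/√DE)).

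Example, 1.88 equal changes, ICC 0.10: DE = 1 + 0.88 × 0.10 = 1.088; √DE = 1.043; α = 6.0%.
Example, 3.91 equal changes, ICC 0.30: DE = 1 + 2.91 × 0.30 = 1.87; √DE = 1.37; α = 15.2%.

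The unequal-size columns are beta-binomial simulations, 10,000 runs per cell, with m_w about 2.76 and 6.72.

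| ICC | 1.88, equal | 1.88, unequal | 3.91, equal | 3.91, unequal |
|---|---|---|---|---|
| 0.05 | 5.5% | 6.0% | 6.7% | 8.3% |
| 0.10 | 6.0% | 6.3% | 8.5% | 11.7% |
| 0.20 | 7.1% | 9.1% | 11.9% | 17.8% |
| 0.30 | 8.1% | 11.6% | 15.2% | 22.8% |

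For equal sizes and ICC 0.10 to 0.30, the 358 changes carry the information of 358/DE = 329 to 283 independent ones at 1.88 per patient, and 277 to 191 at 3.91.

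**Step 3: prophylaxis type partly varying within patient.** Under 4.10.3, a Jales change with no prior test, or with no specific organism on culture, counts as empirical. With half the patients at Jales (assumed) and unequal cluster sizes:
- 30% of Jales changes counted as empirical: 5.8% to 8.2% at 1.88 per patient and 7.1% to 15.4% at 3.91, for ICC 0.05 to 0.30.
- 50% counted as empirical (4,000 runs): 5.4% and 6.4% at 1.9 per patient, and 7.0% and 12.1% at 3.9, for ICC 0.10 and 0.30.

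Monte Carlo error is about √(0.05 × 0.95/4,000) = 0.34 percentage points, so 5.4% is barely distinguishable from 5%.

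**Step 4: covariates that vary freely between procedures.** Rejection stayed between 4.4% and 5.4% in every cell.

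**Step 5: does clustering on patient repair it?** A patient-clustered score test on the fixed-exposure, unequal-size data rejected in 4.6% to 5.3% of runs for ICC 0.05 to 0.30.

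**The case against.** The size is not established, and several points against a large effect are fair:
- No document supports any particular ICC. One retrospective series cited in 1.5.2 found that previous urinary infection was not a risk factor.
- The 3.91 figure comes from a series not described as a cancer cohort. Applied here, it implies that only 92/372 = 25% of patients ever had a change, against 51% in the cancer cohort.
- The exclusions in 4.7 (procedures under treatment for urinary infection, patients on suppressive antibiotics) may remove some of the patients who drive the correlation.
- Crude infection proportions and unadjusted odds ratios do not change; only their stated uncertainty does.

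These limit the size, not the direction.

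Three stronger readings are tempting but not supported:
- **That prophylaxis type is constant within a patient, so the fixed-exposure figures apply.** The 4.10.3 rule sets the type change by change at Jales, the only hospital assigned guided prophylaxis. The inflation is then smaller (step 3).
- **That every risk factor at catheter change is affected.** Factors that move freely between procedures, as laboratory values may, are hardly touched (step 4).
- **That the counts prove repeats.** 358 changes is fewer than 372 patients. Still, having no repeats would need 358/372 = 96% of patients to have exactly one change each. That is implausible given the 90-day schedule and the institution's earlier cohort, which had 93 changes against 87 first passes.

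**Conclusion.** The independence rule is not justified for catheter changes. If patients have repeat changes and within-patient correlation is positive, both of which the protocol leads one to expect, standard errors are too small for guided versus empirical prophylaxis and for patient-level factors. The nominal 5% test then rejects too often.

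Under the assumed ICC of 0.05 to 0.30 and 1.9 to 3.9 changes per patient, the true level is about 5.5% to 23% if prophylaxis type is fixed within patient. It is about 5% to 15% if 30% to 50% of Jales changes count as empirical. The low end is close to nominal, so the problem may prove small; only the study's own data can show that. Confidence is high in the direction and low in the size. First passes are not affected, since procedures and patients match in number.

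**What to change.** Limit the independence sentence to first passes and keep chi-square or Fisher there. For catheter changes, prespecify:
- **One primary model:** logistic GEE with exchangeable working correlation and robust standard errors, clustered on the existing patient identifier. Use it for guided versus empirical prophylaxis, for the p < 0.20 screen and for the multivariable model. A random-intercept model should not be an interchangeable alternative: its odds ratio is conditional on the patient, whereas the GEE odds ratio is marginal.
- **A sensitivity analysis on the first change per patient.** Chi-square or Fisher is valid there and also covers sparse tables.
- **Reporting** of the number of patients with a change and the distribution of changes per patient, so that readers can judge how much clustering there was.

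The cost is a wording change and a re-run on data already linked by patient, with somewhat wider intervals. With about 41 expected infections, the multivariable model should stay small. Clustering on patient does not remove the confounding of prophylaxis type with hospital, which is a separate matter.

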A retrospective cohort carried out at this institution evaluated 180 percutaneous nephrostomies (87 first passes and 93 catheter changes) over a 3-year period. The occurrence of urinary tract infection related to the nephrostomy catheter was verified up to 7 days after the procedures, with 1.2% of urinary tract infection related to the nephrostomy catheter being identified after its first passage and 11.4% after catheter changes ($p = 0.01$)⁴³. In the first passages, there was no statistically significant difference in urinary infection rates when the patient received antibiotic prophylaxis or

not (0% *versus* 1.5%, respectively; $p = 0.999$). In catheter changes, even without statistical significance ($p = 0.146$), the urinary infection rate was 21.4% in those patients who did not receive antibiotic prophylaxis; 14.8% in those who received empirical antibiotic prophylaxis and 6.4% in those who received targeted antibiotic prophylaxis (with antibiotics guided by a previously collected uroculture result)⁴³. Despite the potential bias in results due to its retrospective nature, this study demonstrates a reality in clinical practice and also a possible solution both to prevent urinary infections in this population and to help rationalize the use of antibiotics.

Finally, a prospective study assessed the incidence of urinary tract infection after nephrostomy catheter changes without antibiotic prophylaxis and found that out of 126 catheter change procedures, 13.5% had infectious complications. Just over half (52.9%) required antibiotic treatment and only 1 patient was hospitalized for such treatment, but without threatening the patient's life, according to the authors⁽⁴⁴⁾.

Consequently, there are more doubts than certainties about antibiotic prophylaxis in percutaneous nephrostomy in cancer patients.

Based on what has been said so far, two fundamental questions can be posed. Firstly: would it be necessary to carry out antibiotic prophylaxis for the first passage of the percutaneous nephrostomy catheter to prevent urinary infection related to the procedure? And secondly: can uroculture-guided antibiotic prophylaxis be superior in preventing urinary tract infection when compared to empirical antibiotic prophylaxis after percutaneous nephrostomy catheter changes guided by imaging? These are the questions that guide this research project.

2.

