3. OBJECTIVES

3.1. Primary

- To evaluate the rate of urinary tract infection related to the percutaneous nephrostomy procedure in cancer patients, according to the use of antibiotic prophylaxis at the first catheter passage and subsequent changes, a retrospective cohort and systematic review with meta-analysis will be conducted.

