4.10. Study Conduct, Measurements and Methodology

One of the main aims of this study is to assess the rates of urinary tract infection related to the percutaneous nephrostomy procedure in cancer patients. At the first catheter change, groups will be assessed according to whether or not antibiotic prophylaxis was used. At subsequent catheter changes, groups will be assessed according to the type of antibiotic prophylaxis used (uroculture-guided *versus* empirical).

Patients eligible for the study will be identified when, during follow-up at the Pio XII Foundation, there was an indication for the image-guided percutaneous nephrostomy procedure after due assessment by the urology and/or interventional radiology teams.

The medical records of patients who underwent the procedure from January 2013 to June 2020 at the Jales Cancer Hospital and from January 2014 to June 2020 at the Barretos Cancer Hospital will be retrospectively reviewed using the database provided by the institution itself (SisOnco).

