4.10.2. First pass procedure

This group will be made up of patients who have undergone percutaneous nephrostomy for urinary tract clearance and we will study whether or not antibiotic prophylaxis was recorded in the medical records to be reviewed at these hospitals.

The following laboratory tests will be considered: serum creatinine and urea levels, urine samples for tests such as urine summary (or type I urine) and uroculture with antibiogram.

The proportion of urinary tract infections that developed within 7 days of the procedure will be studied. A procedure-related urinary tract infection is considered to be any report in the medical record of clinical signs and symptoms associated with uroculture results (see definition in item 4.10.4.) and the location of the respective treatment will be documented: outpatient, inpatient or intensive care unit (ICU).

It will be documented whether there is evidence reported in medical records of urinary tract infections or the presence of bladder fistulas prior to the procedure.

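### Catheter changes done without prophylaxis have no stated group: they may be coded as empirical, or left out so that use versus non-use at changes is not estimated in the cohort

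*Protocol*

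**What the plan says.** The primary objective (Protocol 3.1) is to evaluate the rate of procedure-related urinary tract infection "according to the use of antibiotic prophylaxis at the first catheter passage and subsequent changes".

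The groups are defined in several places:

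- **Protocol 4.12, first passage:** "In the first passage, procedures with antibiotic prophylaxis and without antibiotic prophylaxis will be studied". Section 4.10.2 agrees: for the first-pass group, "we will study whether or not antibiotic prophylaxis was recorded in the medical records to be reviewed at these hospitals".
- **Protocol 4.12, changes:** "In catheter changes, procedures with empirical antibiotic prophylaxis and with targeted antibiotic prophylaxis will be studied". Section 4.10.3 names the same two groups.
- **Protocol 4.10:** "At the first catheter change, groups will be assessed according to whether or not antibiotic prophylaxis was used". It continues: "At subsequent catheter changes, groups will be assessed according to the type of antibiotic prophylaxis used", meaning culture-guided versus empirical.
- **Protocol 4.10.3, Jales:** "If the tests are not carried out prior to the procedure", or if the culture shows no specific agent, the change is studied as empirical. The rule does not ask whether an antibiotic was given.
- **Protocol 4.10.3, Barretos:** the empirical prophylaxis entered in the medical records is studied.

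Inclusion (4.6) does not require prophylaxis. Exclusion (4.7) removes procedures done during antibiotic treatment for urinary infection and patients on suppressive therapy, but not changes done without prophylaxis.

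Section 1.5.2.3 reports an earlier cohort at the same institution. At catheter changes, "the urinary infection rate was 21.4% in those patients who did not receive antibiotic prophylaxis; 14.8% in those who received empirical antibiotic prophylaxis", and it was 6.4% with targeted prophylaxis (p = 0.146).

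The SAP names no prophylaxis groups. It has only a general Bonferroni rule for comparing more than two groups.

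**The concern.** An eligible change done without prophylaxis can be among the 358 change procedures (Protocol 4.9), yet the plan does not say where it goes. The analyst has two routes, and each has a cost.

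- **Counted as empirical.** At Jales the default rule allows this for any untested or culture-negative change. The empirical group then mixes treated and untreated procedures, and the targeted-versus-empirical comparison no longer compares two kinds of prophylaxis.
- **Dropped.** The empirical group is not contaminated, but the cohort then gives no estimate of use versus non-use at changes, which the primary objective can be read to require.

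Because the route is not fixed, it could be chosen after the results are known.

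Separately, 4.10 puts the with/without comparison at the first catheter change, while 4.10.2 and 4.12 put it at the first passage. Taken literally, 4.10 gives first changes a different comparison from 4.12 and gives first passages none.

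**Working it through.** **Step 1. Recover the earlier cohort's counts.** Section 1.5.2.3 gives rates only: 21.4% (none), 14.8% (empirical) and 6.4% (targeted), 11.4% overall at changes, from 93 changes. A search over all whole-number splits with a total of at most 93 finds one that rounds to the three rates:

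| Group | Infected / changes | Rate |
|---|---|---|
| None | 3/14 | 21.4% |
| Empirical | 4/27 | 14.8% |
| Targeted | 3/47 | 6.4% |
| Total | 10/88 | 11.4% |

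The total matches the stated 11.4%, and the Fisher-Freeman-Halton exact test on this table gives p = 0.146, the stated value. The counts are still inferred, and 93 − 88 = 5 changes are unaccounted for.

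**Step 2. Share of changes without prophylaxis.** 14/88 = 15.9%. If the same share held here, 358 × 14/88 ≈ 57 changes. That it carries over is an assumption.

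**Step 3. Effect of folding untreated changes into the empirical group.** If a fraction k of the untreated changes is counted as empirical, the group's rate is (4 + 3k)/(27 + 14k). The difference is from targeted, 3/47 = 6.4%.

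| k | Rate in empirical group | Difference from targeted |
|---|---|---|
| 0 | 4/27 = 14.8% | 8.4 points |
| 0.25 | 4.75/30.5 = 15.6% | 9.2 points |
| 0.5 | 5.5/34 = 16.2% | 9.8 points |
| 1 | 7/41 = 17.1% | 10.7 points |

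Odds ratio, empirical versus targeted:

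- k = 0: (4/23)/(3/44) = 2.55
- k = 1: (7/34)/(3/44) = 3.02

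The last row is a ceiling. The default rule in 4.10.3 covers Jales only, and the documents do not give the split of untreated changes by hospital.

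**Step 4. How firm is the direction?** The shift is upward only if untreated changes have a higher infection rate than empirically treated ones. On the inferred counts, 3/14 versus 4/27 is a difference of 21.4 − 14.8 = 6.6 points, with a 95% interval (Newcombe) of about −16 to +34 points and Fisher p = 0.67. The sign is not established. The same rule also sends culture-negative changes to empirical; if these carry a lower risk, they pull the empirical rate down.

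**Step 5. Location of the with/without comparison.** Section 4.10 says first change. Sections 4.10.2 and 4.12 say first passage, and the first guiding question closing 1.5.2.3 asks about first passage. The weight of the text favours first passage.

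**The case against.** The strongest reply is that 4.10.3 studies prophylaxis documented in the records. On that reading an untreated change never enters the empirical group, and the Jales default only sorts type of prophylaxis among treated cases. The guiding question for changes (1.5.2.3) asks only about culture-guided versus empirical prophylaxis, so two groups match it. The systematic review's PICO (4.13) includes with versus without prophylaxis. The wording in 4.10 is probably a slip.

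Much of this stands. A reader might infer that the empirical group is biased as the plan is written, and in favour of targeted prophylaxis. The documents do not support that: misclassification is possible, not stated, and its direction rests on 3/14 versus 4/27. A reader might also infer that use versus non-use at changes goes wholly unanswered. That holds for the cohort only, because the primary objective is assigned to the cohort and the review together. The conflict over where the with/without comparison belongs biases nothing by itself.

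What does not stand is that the text settles the matter. The Jales rule is triggered by a missing test or a culture with no specific agent, and it does not ask for a recorded antibiotic. On the documented-use reading, untreated changes are still eligible and still have no stated place. The collection form (Appendix II) might code them, but it is not in the text available, and the analysis sections do not use such a category.

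**Conclusion.** The point holds in limited form. Eligible catheter changes without prophylaxis have no group in 4.10.3 or 4.12, and the Jales default can place them in the empirical group. If that happens, the illustration puts the empirical rate between 14.8% and at most 17.1%, the difference from targeted between 8.4 and at most 10.7 points, and the odds ratio between 2.55 and 3.02. If they are dropped, that shift does not arise, but the cohort does not estimate use versus non-use at changes.

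These figures assume that the inferred counts are correct and that the earlier cohort's rates and mix apply here; whether the two cohorts overlap is not stated. The gap in the classification is certain. The size and direction of any bias are not.

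This should be corrected, because it concerns the exposure definition in a main comparison and the correction is cheap.

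**What to change.** 1. In 4.10.3 and 4.12, and in the SAP, define exposure at catheter changes as none, empirical or targeted, coded from the antibiotic actually recorded. Keep not recorded as a separate category and report the count in each, by hospital.
2. Apply the Jales default only to changes for which an antibiotic was given.
3. State two contrasts at changes: any prophylaxis versus none, and targeted versus empirical among treated procedures.
4. Reconcile 4.10 with 4.10.2 and 4.12 on whether the with/without comparison is made at the first change or at the first passage.

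The cost is wording and recoding, one extra contrast, and a somewhat smaller empirical group. Separate coding of antibiotics given for other infections would be optional: the listed study variables (4.10.5 and the SAP) cover antibiotics for prophylaxis or for treating urinary infection only, so it may need further chart review.
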